Watkins-Conti Products, Inc., has developed a simple design that solves many of these problems and could provide a simple, inexpensive solution for SUI for many women. The Collapsible Cone-Shaped Intra-Vaginal Urinary Incontinence Support Device (Yoni.Fit) from 100% medical grade silicone, places pressure on the urethral sphincter while supporting pelvic organs, thus eliminating or significantly reducing urine leakage. Inspired by the ring pessary, the simple yet effective design of the collapsible device Yoni.Fit is user friendly, light weight and less difficult to hold in the vagina than the Colpexin. Yoni.fit is believed to assist with strengthening the pelvic floor like the Colpexin while supporting anatomy like the pessary, reducing the need for invasive surgeries altogether.

[figure not shown]
In order to support applications for Small Business Innovation Research funding and for investor funding, Watkins-Conti Products proposes to demonstrate short term efficacy with patients suffering from SUI for reduced or eliminated leakage against a standardized battery of challenges as a primary endpoint. Ease of use and support of anatomy with use of Yoni.Fit will serve as secondary endpoint

Specific Aims-
Aim: Test the acute efficacy of Yoni-Fit in a clinical trial of unselected women with incontinence in a standardized set of challenges performed with and without Yoni-Fit in place.

Protocol

The flow chart for the study is shown in the figure below.

Flow Chart for Feasibility Study

1. Subjects will be recruited in two ways. First, subjects will be referred from the patient bases of two physicians at the OUHSC who treat incontinence. These are [name] of the Department of Obstetrics and Gynecology and [name] of the Department of Urology. The second source will be a campus-wide email announcing the study. Regardless of the method, potential subjects will be referred to [name], a research coordinator for the study who is employed by the Department of Urology.

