2. Potential subjects will be pre-qualified by a 6-item questionnaire, the Questionnaire for Urinary Incontinence Diagnosis (QUID) (4). This questionnaire has 3 questions each referring to the seriousness of Stress Urinary Incontinence (SUI) and of Urge Urinary Incontinence (UUI). Subjects will be accepted if their SUI score is 5 or greater and is greater than the UUI score. For privacy reasons, these scores will not be retained. Subjects will then be given an appointment. Subjects will be instructed to wear comfortable athletic type wear and not to drink any fluid for two hours prior to their appointment.
3. When they appear for their appointment, subjects will be administered the informed consent. All paperwork will be pre-numbered with a code that will link to the subject name. They key will be kept confidential by the Study Coordinator. They will be instructed to empty their bladders and will be given a liter of water or other drink and instructed to drink it over a 15-20 minute time period. An abbreviated patient history will be obtained for the purpose of establishing whether the subject meets the inclusion criteria and is not disqualified by meeting the exclusion criteria. The subject will again fill out the QUID questionnaire. The inclusion criteria are a SUI score of 5 or greater, predominately SUI (SUI score>UUI score) and age between 25 and 65. Exclusion criteria are predominantly UUI, prolapse greater than mild, hysterectomy or other pelvic floor surgery other than a Caesarian section, diabetes, BMI>35 or unable to perform ten

“jumping jack” exercises. Patients will be administered three additional questionnaires in order to compute a Severity Score. These questionnaires are the Urinary Distress Inventory (UDI), Urinary Impact Questionnaire (UIQ) and the Incontinence Severity Index (ISI). The scores will be multiplied together to provide the Severity Score.

4. Patients will then participate in an abbreviated Pad Test. This test has been validated (5). An hour after finishing the liter of liquid, the subject is given a tared incontinence pad, which is then put in place. She then engages in the following mild exercise challenges..
 - a. Stand from sitting 10 times.
 - b. Cough vigorously while standing.
 - c. Bend down to pick up small object.
 - d. Perform ten jumping jacks.

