The subject then will remove pad, place into bag and seal. The Experimenter will then weigh pad. The subjects will be randomized so that half will perform the Abbreviated Pad Test with the Yoni.Fit device in place followed by repeating without the device in place. The other half will perform the challenges in the reverse order.

5. The experimenter will calculate a change in score, which is the weight of the pad worn without the device in place minus the tare weight of the pad divided by the weight of the pad with the device in place minus the tare weight of the pad. In case no urine is released with the device in place, the Improvement Score will be defined as “1000”. A Release Change will also be calculated as the net weight without the device in place minus the weight with the device in place divided by the net weight released without the device in place.
6. Patients will be paid \$100 for their participation.

Data Analysis

After checking the data for correctness, the data analysis will ensue. Descriptive statistics will be calculated and include the mean, median, standard deviation. The improvement scores will be correlated with the symptom scores and demographics to provide a preliminary estimate of how well the YoniFit performs and possibly to identify parameters that predict less than optimal prevention of SUI.

Budget

Item	Amount
Personnel	
[name], PI	\$9,251
[name], Clinical Coordinator	\$3,989
Per subject costs	\$38,250
IRB application and account set-up	\$3,000
Supplies and Miscellaneous Costs	\$1,000
Total direct cost	\$55,490
Clinical trial IDC (30%)	\$16,647
Grand Total cost	\$72,137

Budget Justification

[name] will act as overall PI for this project and will coordinate between Watkins-Conti Products and the OUHSC. He will meet with the clinicians as necessary and weekly with [name] to assess progress and solve any problems. He will also be responsible for preparing the IRB application and for the data analysis and for preparing a report. His cost is calculated on the basis of 1 person-month (8.33% effort) on a University salary of \$80,457 plus 37.98% fringe benefits.

[name] will act as the clinical coordinator. In addition to the per subject costs, she will also assist with preparing the IRB application, talk to patients who do not qualify, coordinate with the physicians and meet with [name]. Her cost is calculated on the basis of a salary of \$28,907 with 10% effort plus 37.98% fringe

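### The plan sets out to test acute efficacy and randomises test order, but Data Analysis names no confidence interval or test of the device effect and states no use of the order

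*Combined protocol and SAP*

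**What the plan says.** Background and Significance says that the sponsor "proposes to demonstrate short term efficacy with patients suffering from SUI for reduced or eliminated leakage against a standardized battery of challenges" and makes this the primary endpoint. Specific Aims says: "Test the acute efficacy of Yoni-Fit in a clinical trial of unselected women with incontinence". The figure in the Protocol section is titled "Flow Chart for Feasibility Study".

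Step 4 of the Protocol randomises the order of the two pad tests: "half will perform the Abbreviated Pad Test with the Yoni.Fit device in place followed by repeating without the device in place". The rest do the tests the other way round.

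The text describes one void and one fluid load before testing. In step 3, "They will be instructed to empty their bladders and will be given a liter of water or other drink"; in step 4, "An hour after finishing the liter of liquid, the subject is given a tared incontinence pad". It gives no second void, further fluid or interval before the repeat test. The flow chart is not shown in the copy available.

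Step 5 defines two scores per woman. The Improvement Score is net pad weight without the device over net weight with it, and "In case no urine is released with the device in place, the Improvement Score will be defined as" 1000. The second score is the relative reduction: "A Release Change will also be calculated as the net weight without the device in place minus the weight with the device in place", over the net weight without it.

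Data Analysis has three elements: a data check, descriptive statistics (mean, median and standard deviation are listed), and a correlation of the improvement scores with symptom scores and demographics. As the sentence is built, the preliminary estimate of performance comes from that correlation. There is no confidence interval, test, significance level or paired comparison, and no mention of order or period. No sample size is stated.

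**The concern.** The aim and the analysis do not meet. Correlating a score with covariates shows which women respond more or less; it does not estimate leakage with versus without the device. The descriptive statistics do estimate it, but without an interval they cannot say how precisely the reduction is known or whether it exceeds chance. Background says the results are meant to support funding applications, so readers will want to know exactly that.

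The second part depends on whether leakage tends to differ between the first and second test. With one stated void and fluid load it could, for example because bladder volume has changed. The order is randomised and will be known for every woman, but the plan does not say that it enters any summary or estimate.

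**Working it through.** The plan gives no sample size, variance or effect size, so it has no statistical figure to reproduce. Every input below is an assumption except those from the Budget.

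**1. Number of women.** Budget per-subject costs of $38,250 divided by $765 per woman = 50. The seven cost items do sum to 765 (120 + 100 + 100 + 20 + 100 + 125 + 200). This N is implied, not stated. If no woman carried the $125 referral fee, 38,250 / 640 = 59.8, so 59 women.

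**2. Is an interval feasible?** For a mean within-woman difference, the 95% half-width is t × SD / √N. With N = 50 this is 0.284 SD. A two-sided 5% paired test has 80% power at (1.96 + 0.84) / √50 = 0.40 SD. An interval or a test is therefore practicable at the size the Budget implies.

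**3. Does the planned SD already give a useful interval?** Not for the Improvement Score. With 5 of 50 women dry with the device and the rest at 2, the mean is (5 × 1000 + 45 × 2) / 50 = 101.8, the SD is 302 and the median is 2. The interval is 101.8 ± 0.284 × 302, or about 16 to 188, which excludes the value held by 45 of the 50 women. A single dry woman gives (1000 + 49 × 2) / 50 = 22.0.

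**4. Period effect and the two ratio scores.** Let second-test leakage be r times first-test leakage, the device useless, the orders balanced and no noise.
- Improvement Score is r (device first) or 1/r (device second); mean (r + 1/r) / 2.
- Release Change is 1 − 1/r or 1 − r; mean 1 − (r + 1/r) / 2.

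On the log scale, ln r and −ln r cancel. On the difference scale, an additive period effect cancels in the same way.

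**5. Period effect and precision.** Assume N = 50, within-test log-SD 0.5 and no dry pads. The SD of the log ratio is √(2 × 0.5²) = 0.707 if period is fitted and √(0.5 + (ln r)²) if order is ignored. The interval width is 2 × 0.284 × SD; at r = 2 with order ignored, 2 × 0.284 × 0.990 = 0.56. Power in grams comes from simulation: 6,000 trials, 25 women per order, true 30% reduction, between-woman log-SD 1.0, rank-sum by order against signed-rank ignoring order.

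| r | Mean Improvement Score, useless device | Mean Release Change, useless device | Log-ratio CI width, order used v ignored | Power in grams, order used v ignored |
|---|---|---|---|---|
| 1 | 1.000 | 0.000 | 0.40 v 0.40 | 85 v 86% |
| 1.25 | 1.025 | -0.025 | 0.40 v 0.42 | 85 v 84% |
| 1.5 | 1.083 | -0.083 | 0.40 v 0.46 | 82 v 78% |
| 2 | 1.250 | -0.250 | 0.40 v 0.56 | 74 v 53% |

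Ignoring order makes the test conservative, not liberal: with a useless device and r = 2, its type I error was 0.5 to 0.7% in the simulations.

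**6. What the rank-based gram estimate measures.** Take test-1 minus test-2 net weight per woman. With an additive period effect p in test 2, this is (without − with − p) if the device comes second and (with − without − p) if it comes first. The gap between the order groups is twice the reduction, and p drops out. Half the Hodges-Lehmann shift is therefore a location-shift estimate, but with skewed leakage it is not the mean reduction. With median leakage 1 unit, mean leakage is exp((1.0² + 0.5²) / 2) = exp(0.625) = 1.87. The mean reduction over the two tests is 1.87 × 0.3 × (1 + r) / 2, which is 0.56 at r = 1 and 0.84 at r = 2. Half the Hodges-Lehmann shift was 0.31 and 0.45. Its halved limits covered the mean reduction in only 56 to 59% of simulated trials.

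**The case against.** The strongest reply is that this is a feasibility study seeking a preliminary estimate, so descriptive statistics suffice. That makes a formal test arguable. It does not dispose of the interval, because the aim and the endpoint are worded as testing and demonstrating efficacy.

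A second reply is that the SD and N let a reader work out an interval. That is true for the mean of a score, but for the Improvement Score the code 1000 makes the result of little use.

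A third reply concerns order, and most of it stands. Balanced randomisation already protects the mean difference against an additive period effect. The planned medians are largely protected under a proportional one: with a true 30% reduction, the pooled median Release Change stayed at 0.29 in simulation at every r. By order at r = 2 the model medians are 1 − 0.7/2 = 0.65 and 1 − 0.7 × 2 = -0.40, so pooling hides the period effect but does not shift the median. Nor is order the main problem with the means: ratio noise alone (log-SD 0.5) takes the mean Release Change from 0.30 to 1 − 0.7 × exp(0.25) = 0.10.

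A reader might infer that leaving order out biases the trial's answer or invalidates it. The documents do not support that. They give no period effect, the flow chart that might show a rest or a second void is not available, and on a difference or log scale the loss is one of precision. A reader might also infer that results by order are ruled out. They are not: the list of descriptive statistics is open-ended, so the accurate statement is that use of order is not stated.

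**Conclusion.** The point holds as a cheap improvement. The firm part is that the plan gives no interval or test for the with-versus-without effect that its aim sets out to test, and that the listed statistics do not supply a useful interval for the Improvement Score. This rests on the text alone, apart from the illustrative counts of dry women.

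The part about order is conditional. A period effect is possible, but its size is unknown. If there is none, using the order gains nothing and costs about 1 point of power in grams. If second-test leakage were doubled, ignoring order would widen the log-ratio interval from 0.40 to 0.56 and would move the null means of the two scores to 1.25 and -0.25. At a ratio of 1.5 the gain in gram power is only about 4 points. These figures rest on the implied N of 50 and on assumed variances and period effects.

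**What to change.** In Data Analysis, name one primary within-woman comparison of net pad weight with and without the device, make it use the randomised order, and report it with a 95% CI. Either option would do:

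- **A, in grams.** Compare test-1 minus test-2 net weight between the two order groups by Wilcoxon rank-sum, and report half the Hodges-Lehmann shift with halved limits. Describe it as a location-shift estimate, not as the mean or median reduction or as an effect averaged over the two tests. If a mean reduction is wanted, report half the difference in group means with its CI. Dry pads need no special code.
- **B, log ratio adjusted for period.** Prespecify a rule for zeros and a sensitivity check on it. The rule matters: with 10% dry pads and a median leak of 10 g, the simulated ratio was 2.17, 1.82 or 1.68 when 0.1, 0.5 or 1.0 g was added.

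Report the Improvement Score and Release Change as descriptive medians, overall and by order, and record the clock time of each test.

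The cost is a few sentences, one time field on the form, one degree of freedom and, if there is no period effect, about 1 point of power in grams (85% against 86%). Neither option removes carry-over that differs between the two orders.

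### Step 5 gives a fixed Improvement Score of 1000 for a urine-free device pad but sets no gram cut-off for dry, so a small non-urine weight gain can remove that score

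*Combined protocol and SAP*

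**What the plan says.** In Protocol step 4, "the subject is given a tared incontinence pad, which is then put in place". The woman does the exercise battery, and then: "The subject then will remove pad, place into bag and seal. The Experimenter will then weigh pad". The test is done once with the device and once without, in randomised order.

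Step 5 builds two scores from the weights. The Improvement Score is the net weight without the device "divided by the weight of the pad with the device in place minus the tare weight of the pad". The exception is the dry case: "In case no urine is released with the device in place, the Improvement Score will be defined as" 1000. The second score is defined as follows: "A Release Change will also be calculated as the net weight without the device in place minus the weight with the device in place". That difference is then expressed as a fraction of the without-device net weight.

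The Data Analysis section says "Descriptive statistics will be calculated and include the mean, median, standard deviation", and plans to correlate the improvement scores with symptom scores and demographics. The paragraph before Specific Aims states the primary endpoint as leakage either lowered or abolished.

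The documents do not say how absence of urine is established, what the balance resolves, what happens to a net weight below zero, or whether the bag is part of the tare or of the later weighing.

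**The concern.** Absence of urine is a statement about the woman, but the plan measures only a weight difference. With no threshold stated, following step 5 literally means that any positive net weight goes into the ratio and only a reading of zero earns 1000. The pad is worn through repeated standing, coughing, bending and jumping jacks, and in one condition after a vaginal device has been inserted. Some weight gain that is not urine is therefore plausible, and every balance has some error.

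The ratio is steepest where the weighing is least informative, with the device-pad net weight near zero. A trivial gain can move a completely dry woman from 1000 to a two-digit score. The mean, the SD and the planned correlations of the Improvement Score would then depend partly on an unstated property of the balance. The part of the primary endpoint that concerns abolished leakage would have no defined reading.

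The without-device pad has the same gap. Eligibility rests on questionnaire scores and not on measured leakage, so a woman who leaks in neither condition can be enrolled.

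**Working it through.** **Inputs.** The two score formulas and the value 1000 come from step 5. I read both weights in Release Change as net weights and apply the division to their difference. The plan has no figure of its own to reproduce: it states no cut-off, balance resolution, expected leakage or expected dry rate. Every loss, gain and resolution below is an assumption.

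**Notation.** W is the true loss without the device, and a is the non-urine gain. The woman is truly dry with the device, so the plan intends an Improvement Score of 1000 and a Release Change of 100%.

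**1. Gain on the device pad only, W = 20 g.** Improvement Score = W/a; Release Change = (W − a)/W.

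| a (g) | Improvement Score | Release Change |
|---|---|---|
| 0 | 1000 (by rule) | 100% |
| 0.1 | 20/0.1 = 200 | 19.9/20 = 99.5% |
| 0.5 | 20/0.5 = 40 | 19.5/20 = 97.5% |
| 1.0 | 20/1.0 = 20 | 19/20 = 95% |

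**2. Same gain on both pads, a = 0.5 g.** Improvement Score = (W + a)/a; Release Change = W/(W + a).
- W = 10 g: 10.5/0.5 = 21 and 10/10.5 = 95%.
- W = 2 g: 2.5/0.5 = 5 and 2/2.5 = 80%.

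**3. No urine on either pad.** With gains of 0.3 g without the device and 0.1 g with it, the Improvement Score is 0.3/0.1 = 3 and Release Change is (0.3 − 0.1)/0.3 = 67%. That is an apparent benefit with no leakage at all.

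**4. Effect on the mean Improvement Score.** The Budget implies 38,250/765 = 50 subjects if all are charged at the full per-patient rate. Suppose 25 are truly dry with the device, the other 25 score 2, and a misread dry pad scores 21 (as in 2, W = 10 g).
- None misread: (25×1000 + 25×2)/50 = 501.
- Half misread: (12.5×1000 + 12.5×21 + 25×2)/50 = 256.
- All misread: (25×21 + 25×2)/50 = 11.5.

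**5. How often a dry pad reads exactly zero.** The gain is taken as normal and rounded to the balance resolution (simulated).

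| Assumed gain | 0.01 g balance | 0.1 g balance | 1 g balance |
|---|---|---|---|
| mean 0.3 g, SD 0.2 g | 0.6% | 6.5% | 84% |
| mean 0, SD 0.05 g (balance error only) | 8% | 68% | about 100% |

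In the second row, readings other than zero are about equally often positive and negative. A negative device-pad reading gives a negative ratio when the other net weight is positive, and step 5 has no rule for it.

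**6. The bag.** Suppose an untared 5 g bag were weighed, with true losses of 10 g without and 2 g with the device. The Improvement Score would be (10 + 5)/(2 + 5) = 2.1 instead of 10/2 = 5.0. Release Change would be (15 − 7)/15 = 53% instead of 8/10 = 80%. No pad could read zero.

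**The case against.** The strongest reply is that step 5 speaks of urine, not of a reading of zero, and a sensible experimenter on a coarse balance would record most dry pads as zero. Table 5 supports this: the chance runs from under 1% to about 100% depending on inputs that the plan does not give. A reader might infer that the plan imposes a cut-off of exactly zero and that most dry women will be scored as leakers. The documents support neither. Zero is only the effective cut-off, because net weight is the sole measure described, and the misreading rate is unknown.

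A reader might also infer that the bag is in fact weighed untared. The text says that the pad is weighed and that the pad's tare is subtracted, which can be read as like compared with like. The bag is an ambiguity, not a shown error.

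It can also be said that the large figures come from the jump to 1000 and that Release Change is little affected. That stands at a 20 g loss; at 2 g with 0.5 g on both pads it is less reassuring. Further, no responder proportion is planned, and moisture on the device pad alone makes the device look worse, so that case creates no false efficacy. Both statements are correct, though the case of no urine on either pad shows that the error need not always run that way.

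Finally, the pad test is cited as validated and the source may give a detection limit. None is carried into the protocol, and the source cannot be checked here.

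**Conclusion.** The point holds as a gap in an operational definition that affects a planned score. Under step 5 as written, any positive net weight, however small, replaces 1000 by a ratio. The Improvement Score, its mean and SD, and its planned correlations are therefore sensitive to balance resolution and non-urine moisture. For a truly dry woman who loses 20 g without the device, assumed gains of 0.1 to 1.0 g take the score from 1000 to between 200 and 20, while Release Change loses 0.5 to 5 percentage points. The sizes rest wholly on assumed gains and losses, and the documents do not allow a misreading rate to be estimated. A reader might conclude that the trial cannot show benefit. That does not follow, because a reduction in leakage remains readable, most clearly through Release Change when the loss without the device is large. The point is worth correcting before the first subject because the rule is cheap to state and difficult to choose impartially once the weights are known.

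**What to change.** **Step 4.** Tare each pad together with its own numbered bag, and weigh the sealed pad plus bag after the test. State the balance resolution.

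**Step 5.** Before the first subject, fix a cut-off d in grams from repeat weighings of unused pads plus a stated moisture allowance. Treat a net gain at or below d, including any negative value, as dry, and apply this to both pads.

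**Data Analysis.** Report the proportion dry with the device among women wet without it as the result for abolished leakage. Show that proportion, the Improvement Score and Release Change at several values of d, including 0. Count women dry on both pads separately: the rule for a dry device pad would otherwise give them 1000, and their Release Change would be zero over zero.

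**Cost.** A few sentences of protocol text and some repeat weighings. There are two downsides. True leaks of d or less are called dry, which favours the device. The jump to 1000 also stays, now at d: with d = 1 g (an example only) and 20 g lost without the device, a 1.0 g gain scores 1000 and a 1.1 g gain scores 20/1.1 = 18. The display over several d exposes both but removes neither.

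### Release Change omits the tare correction for the with-device pad; read literally, every value is too low by the ratio of pad tare to leak without the device

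*Combined protocol and SAP*

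**What the plan says.** Step 5 of the Protocol section defines two measures of leakage.

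- **Improvement Score.** This is a ratio of pad weights, without the device over with it. The tare is removed from the without-device pad, and the result is "divided by the weight of the pad with the device in place minus the tare weight of the pad". A woman who releases no urine with the device is assigned 1000.
- **Release Change.** This starts from the net weight without the device, and the rule continues "minus the weight with the device in place divided by the net weight released without the device in place". The word *net* qualifies the without-device weight both times it appears. It does not qualify the with-device weight.

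On weighing, step 4 states that "the subject is given a tared incontinence pad, which is then put in place", and after the exercises that "The Experimenter will then weigh pad". Neither sentence says whether the recorded figure is gross or net. No tare weight, expected leak or worked example appears anywhere in the document.

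For the analysis, the Data Analysis section states that "The improvement scores will be correlated with the symptom scores and demographics". It does not mention Release Change by name.

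**The concern.** Release Change is meant to be the proportion of leakage that the device prevents: 1 for a woman kept fully dry, 0 for no effect. If the with-device pad enters at gross weight, the pad's own mass is counted as urine leaked with the device. The value then depends on how heavy the pad is as well as on how well the device works.

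Reduced or eliminated leakage is the study's primary endpoint, and step 5 supplies only two measures of it. The Improvement Score depends on an assigned value of 1000 for women who are dry with the device. Release Change needs no such code for them, so its definition should be exact.

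The error would not be the same for everyone. For a given pad it is largest in women who leak least. If a miscalculated Release Change were related to symptom severity, part of any association would come from the pad weight.

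**Working it through.** **Inputs.** The two definitions come from step 5. The plan states no Release Change value, so there is no figure to reproduce. All weights below are assumptions, shown over a range.

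**Notation.** W = net leak without the device; D = net leak with the device; T = tare of the with-device pad. The gross with-device weight is D + T.

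**Step 1: what *weight* means in step 5.** In the Improvement Score, the with-device pad weight is the quantity from which the tare is then subtracted, so there it is a gross weight. If the recorded weight were already net, that formula would remove the tare twice. On the step's own usage, the unqualified with-device weight in Release Change is therefore gross.

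**Step 2: the two readings.**
- Literal: (W − (D + T))/W = 1 − (D + T)/W
- Net in every term: (W − D)/W = 1 − D/W
- Difference, literal minus net: −T/W, for every woman with W > 0

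**Step 3: a woman dry with the device (D = 0).** The net formula gives 1.00 for any W > 0. The literal formula gives 1 − T/W:

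| Assumed T | W = 5 g | W = 10 g | W = 20 g | W = 50 g | W = 100 g |
|---|---|---|---|---|---|
| 5 g | 0.00 | 0.50 | 0.75 | 0.90 | 0.95 |
| 20 g | −3.00 | −1.00 | 0.00 | 0.60 | 0.80 |
| 40 g | −7.00 | −3.00 | −1.00 | 0.20 | 0.60 |

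For example, T = 20 g and W = 50 g gives 1 − 20/50 = 0.60. The value is zero when T = W, negative when T > W, and positive but below 1.00 when T < W.

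**Step 4: a partial effect.**
- W = 10 g, D = 2 g: net formula 1 − 2/10 = 0.80. The literal formula with T = 20 g gives 1 − 22/10 = −1.20.
- W = 50 g, D = 10 g: net formula 1 − 10/50 = 0.80. The literal formula with T = 20 g gives 1 − 30/50 = 0.40.

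The same proportionate benefit gets different scores because T/W differs (20/10 = 2.00 against 20/50 = 0.40).

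**Step 5: no effect (D = W).** The net formula gives 0. The literal formula gives −T/W; with T = W = 20 g this is −1.00.

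**Step 6: no leak without the device (W = 0).** Both readings divide by zero. Step 3 of the Protocol sets entry by questionnaire score, age and exclusion criteria and requires no minimum leak on the pad test, so this case can occur.

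**The case against.** The strongest reply is that this is one dropped word whose meaning is plain. The pad is described as tared. The formula just before removes the tare from both pads. *Net* can be read as carrying over to the parallel term, and a measure named for release would not sensibly include the pad's own mass. The experimenter already needs the net with-device weight for the Improvement Score. The plan checks the data before analysis, and a dry woman with a strongly negative score would be noticed. Any slip could be corrected from the pad and tare weights. The Data Analysis section names only the improvement scores, so it is unclear whether Release Change enters the correlations at all.

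Most of this stands, and it is why the point is of low severity. It does not make the written rule correct: two formulas in one step still treat the same pad differently, and someone following the text exactly would get the wrong number.

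A reader might also object to the missing brackets in the Release Change sentence. That does not support a separate criticism. The Improvement Score sentence has none either, and both can be read sensibly as a difference over a net weight.

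**Conclusion.** The Release Change definition is wrong as written and should be corrected, at low severity. Read literally, it understates every value by T/W, and a woman dry with the device can never reach 1.00.

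A reader might infer that the rule always gives zero or negative change for a dry woman, or that it reverses the apparent device effect. The documents do not support that. The dry woman's score is zero or negative only if the tare is at least her leak without the device, and neither quantity is stated. With an assumed 20 g tare, the score runs from −3.00 at a 5 g leak to +0.80 at 100 g, so the sign depends on figures the plan does not give. Nor do the documents show that any value will be miscalculated, because the intended formula can be inferred.

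The size of the error rests on the assumed weights. The direction of the error and its form, −T/W, follow from the wording alone.

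**What to change.** Insert *net* before the with-device weight in step 5, or state the formula with symbols:

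- W = without-device pad weight minus that pad's own tare; D = with-device pad weight minus that pad's own tare.
- Release Change = (W − D)/W.
- When W = 0, Release Change is undefined; report the number of such women separately.

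Leave the Improvement Score and its existing value of 1000 for D = 0 as they are; this correction does not touch them.

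The cost is one or two lines of protocol text. No extra measurement or procedure is needed, because the Improvement Score already requires both pad weights and their tares.
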